### **2. Study Overview**

Part 2 of the Sleep-Disordered Breathing, Obesity and Pregnancy Study (SOAP2) is the continuation of a prospective observational study of the interplay between sleep-disordered breathing (SDB), obesity and cardiovascular risk factors in pregnancy. Our central hypothesis is that SDB is an effect modifier that increases maternal cardiovascular risk and placental hypoxic injury in obese pregnant women, and that CPAP treatment during pregnancy results in an improved cardiovascular risk and placental profile. To test this hypothesis, our cohort includes obese women with and without SDB. Refer to the table below and sections 1.1-1.4 for a discussion of the protocol. Modifications to this protocol are made only with approval from the IRB and IDSMB.

After a screening process, eligible participants are scheduled for two clinic visits, one during the second trimester (14-20 6/7 weeks) and the other during third trimester (28-31 6/7 weeks). Each visit begins with a questionnaire followed by an overnight polysomnogram (PSG). The following morning, clinical measurements are taken, maternal bloods are collected, a uterine artery Doppler is performed, and non-invasive cardiac output monitoring (NICOM) is performed to measure cardiac function and output.

Participants with severe apnea at the first clinic visit (i.e., AHI estimate  $\geq 50$ ) are withdrawn from the study. Those without SDB (i.e., AHI estimate  $< 5$ ) are assigned to a control group for observation only. Participants with SDB (i.e., AHI estimate 5-49) are randomly assigned to receive CPAP or general sleep hygiene information. CPAP units include a modem that transmits data back to the study team. Data collection points and related forms are discussed in Chapter 5.

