In summary, analyses would begin by describing the baseline characteristics by randomly assigned treatment group. Either parametric (t-test) or nonparametric (Wilcoxon test) analyses would be used to compare continuous characteristics and chi-square tests would be used to compare discrete characteristics across randomly assigned treatment groups. The analyses would be carried out based on intention to treat, but exploratory analyses would be conducted on the per protocol subgroup. The treatment effects of sleep hygiene vs. active CPAP on the vector of cardiovascular risk factors would be compared with multivariate analysis of variance (MANOVA). If differences in baseline characteristics are observed, the characteristics would be included in the MANOVA to control for the potential confounding effects. This analytic plan would be repeated in the per-protocol subgroup. The MANOVA model would be fit with main effects for treatment group and an indicator of the level of compliance as well as the two-way interaction. Additionally, ANOVA and X^2 analyses would be used to examine intergroup differences between Time 1 and Time 2 assessments among all the groups. The assumptions of all analyses (e.g., normality of residuals) would be investigated. If assumptions are violated, transformations of the data would be investigated. If adequate transformations cannot be identified, nonparametric approaches would be utilized.

The revised design would have two impacts on the study design. First, would be a reduction in power of the first comparison. The second would be the size of the effect that can be estimated in the modified design analysis; the detectable effect size would be larger (1.52, assuming 80% power, a type I error rate of 0.05, a two-sided alternative hypothesis, with four outcomes variables in the MANOVA). However, given that Aim 2 and 3 are designed as a pilot study, the size of the effect should not be a concern since the goal of the study is not to definitively determine effectiveness, but rather determine the feasibility of a CPAP trial in pregnancy and see if a treatment effect is possible to consider for a larger study. To that end, any modification that leads to increased adherence to treatment would be of great value to this study, as well as future investigations.

D. Budget

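### The revised Aim 2 and Aim 3 treatment comparisons are planned as significance tests only, with no per-outcome arm difference, direction or confidence interval

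*SAP*

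**What the plan says.** Under SAP section C (Analysis Plan), the effects of sleep hygiene and active CPAP "on the vector of cardiovascular risk factors would be compared with multivariate analysis of variance (MANOVA"). The analysis is by intention to treat. It is repeated in the per-protocol subgroup, with a compliance indicator and its interaction with treatment. Baseline characteristics enter the model only if they are seen to differ between arms. ANOVA and chi-square tests are added for Time 1 to Time 2 differences among all the groups. Section B says that Aim 3 follows the same construct, with the placental profile as the outcome.

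The SAP gives one magnitude for this comparison: "the detectable effect size would be larger (1.52"). The figure is for a two-sided test at alpha 0.05 and a power of 80%, and the model is specified "with four outcomes variables in the MANOVA". The SAP does not name the scale of the 1.52, and it treats effect size as no concern because this is a pilot. The pilot is meant to "determine the feasibility of a CPAP trial in pregnancy and see if a treatment effect is possible to consider for a larger study". The hypothesis in both manuals (section 2, Study Overview) is directional: "CPAP treatment during pregnancy results in an improved cardiovascular risk and placental profile".

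**The concern.** A two-group MANOVA answers one question: is there evidence that the two mean vectors differ in any direction? Its p-value has no sign and no size for any single outcome. Improvement in one measure with worsening in another can count as much as improvement in both, or more. The planned ANOVA and chi-square analyses look at outcomes singly. But they too are described only as tests, they cover all the groups rather than the randomised contrast, and no estimate or interval is named.

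The planners of a larger trial need to know, for each outcome, how large the arm difference might be, in which direction, how uncertain it is, and what SD to plan with. If the pilot reports only p-values, it can end without that information even though the data to supply it were collected.

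**Working it through.** **Inputs from the SAP.** 18 participants per arm (section B, Aim 2); four outcomes, two-sided alpha 0.05, 80% power and a detectable effect of 1.52 (section C).

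**Assumptions, because the documents give no figures.** True shifts of 0.3 or 0.4 SD per outcome; equal correlation ρ of 0 or 0.3 between outcomes signed so that benefit is positive; a Visit 1 to Visit 2 correlation of 0.6; no dropout.

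**Step 1: the plan's own figure.** A two-group MANOVA is Hotelling's T². It is tested as F with p and N − p − 1 degrees of freedom, and its noncentrality is λ = n₁n₂/(n₁+n₂) × D², where D² is the squared Mahalanobis distance between arms. Here the degrees of freedom are 4 and 31, the critical F is 2.68, and n₁n₂/(n₁+n₂) = 324/36 = 9.

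- Exact 80% power needs D² = 1.54 (D = 1.24).
- 1.52 read as D²: λ = 9 × 1.52 = 13.68, power 79.3%.
- 1.52 read as D: λ = 9 × 1.52² = 20.79, power 94.1%.

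Of these two readings, only the squared distance fits 18 per arm. On that reading the plan's effect size has no sign and no per-outcome value.

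**Step 2: power under a consistent benefit and a mixed profile.** For shifts d and equal correlation ρ,

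D² = [Σd² − ρ(Σd)²/(1 + 3ρ)] / (1 − ρ).

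| Shifts (SD) | ρ | D² | λ = 9D² | Power |
|---|---|---|---|---|
| +0.4 on all four | 0 | 0.640 | 5.76 | 39% |
| +0.4 on all four | 0.3 | (0.64 − 0.3×2.56/1.9)/0.7 = 0.337 | 3.03 | 22% |
| +0.3 on all four | 0 | 0.360 | 3.24 | 23% |
| +0.3 on all four | 0.3 | (0.36 − 0.3×1.44/1.9)/0.7 = 0.189 | 1.71 | 14% |
| +0.4 on three, −0.4 on one | 0.3 | (0.64 − 0.3×0.64/1.9)/0.7 = 0.770 | 6.93 | 47% |

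At ρ = 0 the signs make no difference: three benefits and one harm also give 39%. At ρ = 0.3 the test is about twice as likely to be significant for the mixed profile (47%) as for the uniform improvement that the study hypothesises (22%).

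**Step 3: what an interval would show.** The 95% CI half-width for one outcome, in SD units, is t × √(1/18 + 1/18).

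- Unadjusted, 34 df: 2.032 × 0.333 = 0.68 SD.
- Adjusted for the Visit 1 value at correlation 0.6, 33 df: 2.035 × 0.333 × √(1 − 0.36) = 0.54 SD.

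These intervals are wide. They still show which effects the data leave open, in which direction and for which outcome.

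**The case against.** **The MANOVA is not the only analysis, and it is not uninformative.** A reader might infer that the pilot cannot show a treatment effect at all. The documents do not support that. A significant MANOVA signals some difference, the fitted model contains group means and a residual covariance matrix, and outcomes are also examined singly. This stands. The gap is that nothing commits the team to report per-outcome arm differences with their precision.

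**Nothing says that the next step depends on p < 0.05.** A reader might infer that a non-significant result would end the line of research. The SAP contains no such rule and says that the study is not meant to settle effectiveness. This stands too. The point is only that the planned output gives little help with that judgment.

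**It is a pilot.** Feasibility is the first stated goal, and Aim 2 also describes adherence. Neither is touched here. But if effectiveness is not the question, a significance test is the less useful main output, so this argues for estimates.

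**Estimates may be specified elsewhere.** Section 1 of each manual refers to a separate Protocol for the statistical models, and the SAP describes its plan as a summary. That document was not supplied, so the gap is established only for the manuals and the SAP. The SAP is, however, where the revised Aims 2 and 3 are laid out.

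**Conclusion.** The point holds as a cheap improvement. In the supplied documents the revised Aim 2 comparison, and Aim 3 by the same construct, consist of significance tests without a per-outcome arm estimate, direction or interval. That is a poor match for a directional hypothesis and for the second stated goal.

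The powers of 39% and 22%, against 47% for a mixed profile, rest on assumed effects and correlations, on four outcomes as the SAP states, and on complete data from 36 participants. Other assumptions move the figures. They do not change the fact that the test has no sign. The figures cover only the sleep-hygiene comparison; for the 45 randomised against sham, an assumed 22/23 split gives an unadjusted 95% half-width of about 0.60 SD.

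**What to change.** In SAP section C, make the main Aim 2 result, for each outcome in the MANOVA, the between-arm difference at Visit 2 adjusted for that outcome's Visit 1 value, with a 95% CI. Adjust whether or not a baseline imbalance is seen. Name the four outcomes and the favourable direction of each; Table 1, as it can be read, shows three primary measures. Report the residual SDs and the between-outcome correlations, and keep the MANOVA p-value as supporting. For Aim 3, report the corresponding arm difference with 95% CI for each placental outcome, without Visit 1 adjustment, because the placenta is examined only after delivery.

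Do not turn the intervals into a rule to go on whenever a worthwhile benefit lies inside them. If 0.4 SD counted as worthwhile, a treatment with no effect would pass for a given outcome about 80% of the time at a half-width of 0.68 SD (SE 0.68/2.03 = 0.33; Φ(0.28/0.33)), and about 70% at 0.54 SD (SE 0.27; Φ(0.14/0.27)).

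The cost is slightly more analysis work and several wide intervals in place of one test. No extra participants, visits or measurements are needed.

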- Completion of the Sleep Study (SS) form. During the night, SBNC personnel review the participant's polysomnography (PSG) data to calculate an apnea-hypopnea index (AHI) estimate, using AASM 2012 rules. The AHI estimate at the first visit determines eligibility for randomization (see below). If a sleep study is not completed successfully – either because a participant refuses or there is a medical reason or technical problem – SBNC personnel should report this on the SSA and also notify the Study Coordinator. (Note: sleep studies are formally scored later on but these scores are recorded on the SBNC's "Harmony System," not REDCap.)
- Randomization (Visit 1 only). Participants with an AHI estimate 5-49 and who agree to be randomized are randomized by the Study Coordinator to CPAP or Sleep Hygiene for the treatment phase of the study (see "Randomization," below). For those randomized to CPAP, the assignment date, unit number, mask type, and other details are recorded on Group Assignment (GRP) form, and

use and care instructions, included in the case, are presented. For those randomized to Sleep Hygiene, general information is provided.

- Clinical measurements, maternal bloodwork, uterine artery ultrasound and NICOM data. After the PSG, participants are escorted by the Study Coordinator back to Magee. Clinical measurements (vitals, height, weight and waist, hip and neck circumference) are taken using the SOAP2 Tanita Protocol (see Appendix), along with three measures of blood pressure, and recorded on the Clinical Measurement (CM) form; fasting blood is drawn for cardiovascular risk profiles and documented on the Maternal Blood (MB) form; and a uterine artery (UA) Doppler is performed. Blood is processed and then stored for future batched testing. Non-invasive cardiac output monitoring (NICOM) is performed to measure cardiac function and output over a small interval of time (5-10 minutes).
- The Study Coordinator also takes this opportunity to review the Sleep Log, to see if there are any unusual responses, and the Sleep Questionnaire, to see if any responses are missing, asking the participant for clarification or additional information, as appropriate. In addition, during visit 2, the Study Coordinator asks CPAP participants whether all of the equipment is the same as what was originally issued and confirms that all components are still correctly labeled.

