### 5.7. Participant Compensation

All participants are eligible to receive up to \$550 for completing the following procedures:

- PSG (clinic visits 1 and 2):  $\$150 \times 2 = \$300$
- Maternal bloods (clinic visits 1 and 2):  $\$50 \times 2 = \$100$
- Uterine artery Doppler (clinic visits 1 and 2):  $\$75 \times 2 = \$150$

In addition, randomized participants are eligible for the following payments:

- Apnea survey (delivery/post-delivery): \$25
- CPAP compliance incentive (for CPAP participants only): \$10/week
- CPAP return (for CPAP participants only) (delivery/post-delivery): \$40

The Clinical Team uses the web-based WePay™ card payment system to disburse payments to participants. In addition, free parking is provided at Magee and WPIC, for sleep studies.

---

 Compliance is defined as using the CPAP a minimum of 4 hours per day for at least 5 out of 7 days.

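### Aim 2 MANOVA adjusts for baseline only when an arm difference is 'observed', and does not fix the outcomes' Visit 1 values as covariates

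*SAP*

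**What the plan says.** The rule is in SAP section C (Analysis Plan), in the paragraph on revised Aims 2 and 3. Baseline is first tested by arm: "Either parametric (t-test) or nonparametric (Wilcoxon test) analyses would be used to compare continuous characteristics", with chi-square tests for discrete ones. Then: "If differences in baseline characteristics are observed, the characteristics would be included in the MANOVA to control for the potential confounding effects". No significance level, size of difference or list of variables is attached; the only 0.05 in the section belongs to the detectable effect size. The model terms named are treatment, a compliance indicator and their interaction.

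Visit 1 values have one other stated use, a separate additional analysis: "ANOVA and X^2 analyses would be used to examine intergroup differences between Time 1 and Time 2 assessments among all the groups". If assumptions fail, "If adequate transformations cannot be identified, nonparametric approaches would be utilized". The section does not say whether the MANOVA vector holds Visit 2 values or changes.

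The SOAP2 manual shows that the Visit 1 values will exist. Of each clinic visit, section 2 (Study Overview) says "The following morning, clinical measurements are taken, maternal bloods are collected, a uterine artery Doppler is performed". Section 5.2 adds that "fasting blood is drawn for cardiovascular risk profiles and documented on the Maternal Blood (MB) form". Section 5.7 pays for "Uterine artery Doppler (clinic visits 1 and 2" and for "Maternal bloods (clinic visits 1 and 2".

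**The concern.** In a randomized comparison any baseline difference between arms is chance. Testing for one does not find the variables that predict outcome, and prediction of outcome is what makes a covariate worth having. The usual best predictor of a Visit 2 value is the same measurement at Visit 1. Here that is taken the morning after the first sleep study, before any night on assigned treatment. Under the stated rule it enters only when the arms happen to differ on it, and the reader cannot tell how large a difference counts.

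The comparison has 18 women per arm, and the SAP accepts a larger detectable effect than before. One purpose of the pilot is to see whether a treatment effect worth taking to a larger trial is plausible. Precision that costs no extra data matters for that purpose.

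**Working it through.** **Inputs from the SAP (sections B and C):** 18 versus 18; four outcomes; two-sided 0.05; 80% power; detectable effect 1.52.

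**Assumptions, not in the documents:** normal data; Visit 2 values as the outcome; four mutually independent outcomes, each with a Visit 1 value; Visit 1 to Visit 2 correlation rho of 0, 0.3, 0.5 or 0.7; equal effects on all four outcomes; no compliance term.

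**1. The plan's own figure.** For a two-group MANOVA with four outcomes, F has 4 and 36 − 4 − 1 = 31 df. Its noncentrality is (18 × 18 / 36) × D² = 9 × D², where D² is the squared Mahalanobis distance.
- Reading 1.52 as D²: 9 × 1.52 = 13.68, power 79.3%. This reproduces the plan.
- Exactly 80% needs noncentrality 13.894, so D² = 13.894 / 9 = 1.544, or √(1.544 / 4) = 0.62 SD per outcome.
- Reading 1.52 as D gives power 94.1%, which does not fit.

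**2. What the Visit 1 value can offer.** Adjusting an outcome for its own Visit 1 value multiplies residual variance by 1 − rho²: 1, 0.91, 0.75 and 0.51 at the four correlations. The cost is one degree of freedom per outcome and a small loss from chance imbalance.

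**3. How often the plan's rule acts.** If 'observed' means p<0.05, the chance that at least one of four independent Visit 1 values triggers is 1 − 0.95⁴ = 18.5%. In the other trials or so, roughly four in five, the analysis is unadjusted.

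**4. Joint power by simulation at D² = 1.544.** Under the plan's rule, any triggered Visit 1 value enters every equation. The own-value test combines the four adjusted treatment estimates b in a Hotelling-type statistic T² = b′V⁻¹b, with V built from the residual covariances of the four models. F = T² × 30 / (33 × 4) is referred to 4 and 30 df (33 = 36 − 3; 30 = 33 − 4 + 1).

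| Analysis, joint power (%) | rho 0 | 0.3 | 0.5 | 0.7 |
|---|---|---|---|---|
| No adjustment | 80 | 80 | 80 | 80 |
| Plan's rule, p<0.05 | 78–79 | 78–79 | 78–80 | 79–80 |
| Each outcome always adjusted for its own Visit 1 value | 78 | 83 | 90 | 98 |
| One MANCOVA with all four Visit 1 values | 73 | 77–78 | 85–86 | 96 |

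The plan's rule recovers 0 to 15% of the own-value gain under the p<0.05 reading, across the outcome correlations and effect patterns tried. If 'characteristics' excludes the outcomes' Visit 1 values, it recovers none.

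**5. Type I error.** Under the plan's rule (p<0.05) it is 5.0, 4.5, 3.9 and 3.1% at the four correlations. For the own-value joint test it is just under 5%.

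**6. Separate tests in place of a joint test.** Four own-value tests at 0.05 each give about an 18% chance of at least one false positive. With Bonferroni, power to find at least one effect is about 65, 70, 78 and 92%. That is below the unadjusted 80% up to about rho 0.5.

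**7. If the vector is change.** The variance of a change is 2(1 − rho) times that of a Visit 2 value: 2, 1.4, 1.0 and 0.6. Effective D² is then 0.77, 1.10, 1.54 and 2.57. Unadjusted power is 46.8, 63.5, 80.0 and 96.3%.

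**The case against.** **Stronger readings that the documents do not support.** A reader might infer that choosing covariates by baseline test makes the treatment test invalid or creates false positives. The simulated type I error is at or below 5%, so it does not. A reader might also infer that Visit 1 values go unused. The Time 1/Time 2 analysis uses them, but as an addition to the treatment MANOVA. Nor can one conclude that fixed adjustment is specified nowhere. The paragraph is a summary inside a design-change request, and section 1 of the SOAP2 manual says the statistical models are in a Protocol that is not among the supplied documents.

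**The case against acting.** The correlation is unknown, and the visits are weeks apart (14 to 20 6/7 and 28 to 31 6/7 weeks). At rho 0.3 the gain over no adjustment is only 2 to 3 points, and at zero there is a small loss. If the vector is change, most of the deficit at rho 0.7 disappears (96 against 98%). Four outcomes with Visit 1 values is itself an assumption, since Table 1 as supplied names three primary measures. The trial component is a pilot whose main aim is feasibility. Replacing the single MANOVA with separate outcome tests would also introduce a multiplicity problem that the plan does not have.

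**What stands.** All of this limits the weight of the point. The multiplicity objection also decides the form of the fix, because the gains belong to a joint test and require one. None of it shows that waiting for an observed difference is a better way to choose covariates.

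**Conclusion.** The point holds as one of efficiency and pre-specification, to be considered rather than required. If 'observed' means p<0.05, the plan's rule leaves joint power at about 78 to 80% whatever the correlation. Fixed own-value adjustment in one joint test gives about 78, 83, 90 and 98% at rho 0, 0.3, 0.5 and 0.7. The benefit is therefore negligible at rho of 0.3 or below and material from about 0.5.

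The p<0.05 reading is the natural one, because the tests are named just before the rule, but the SAP attaches no level. A looser trigger would recover more of the gain at high rho, so the unstated threshold itself matters. The figures rest on the assumptions listed in the working. If the vector was meant to be change from Visit 1, the gain is much smaller at high rho and larger at low rho.

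The point does not extend to Aim 3 placental outcomes, which have no Visit 1 value.

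**What to change.** Replace the conditional sentence in SAP section C with:

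> The Visit 2 values of the Aim 2 outcomes measured at both visits are compared between randomized arms in one joint test at two-sided 0.05, with each outcome adjusted in all cases for its own Visit 1 value (same transformation, or ranks, at both visits). Per-outcome estimates with confidence intervals are supportive. No covariate is chosen from tests of baseline differences.

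The joint test is mandatory. The Hotelling-type test in the working is one workable form. A single MANCOVA with all four Visit 1 values is standard software, but at rho of about 0.3 or below it has less power than both no adjustment and the plan's own p<0.05 rule.

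**Cost:** no new data, one degree of freedom per outcome, a little code for the joint test, and a rule for participants with no Visit 1 value. If rho is near zero, about 1 to 2 points of power are lost against no adjustment.

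If the full Protocol already fixes these covariates, align section C with it and nothing further is needed.

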#### Instructions: WePay

1. Log on at <https://wepay.upmc.com/WP>
2. Select "Make a Payment"
3. Pick a known participant or search for or create a new participant
4. Activate a new card for new participants or select the payment card for return participants
5. Enter compensation, reimbursement and participant ID
6. Select "Continue" to print a receipt for the participant

---

 Compliance is defined as using the CPAP a minimum of 4 hours per day for at least 5 out of 7 days.

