University of Pittsburgh

Office of Clinical Research, Health Sciences

[name]
[name]
[name]
[contact]
[contact]

Grant No: R01HL120354

January 24, 2017

[name]
Department of Obstetrics, Gynecology and Women's Health
Division of Maternal-Fetal Medicine
Magee-Women's Hospital of UPMC
[name]
[name]

Dear [name],

On Friday January 20, 2017, the Institutional Data and Safety Monitoring Board (IDSMB) of the Office of Clinical Research (OCR), Health Sciences held a teleconference to discuss the proposed modification for your study entitled "Sleep Disorder Breathing, Obesity and Pregnancy (SOAP) Study" IRB Number: PRO13080159.

The DSMB supports your proposed study modification. The proposed modification will not change subject safety and will still continue to contribute meaningful data.

We look forward to your next study update in May 2017.

Sincerely,

A handwritten signature in black ink that reads "[name] MD".

[name]
Chair of the IDSMB Committee

Request: Modify design (pertinent to Aims 2 and 3) so that the arms are auto-CPAP vs an attention control instead of sham CPAP.

In summary, we propose this swap occur after we have randomized 45 individuals under the current design with a plan to randomize another 36 individuals after we switch to the unblinded and unmasked design. Those not randomized to CPAP would be informed of their SDB diagnosis, both verbally and also in a handout/letter. This proposed change in the control arm is being proposed because we believe it will enhance compliance with CPAP. The request is NOT being made based on any safety or risk considerations regarding the current vs. proposed modified design. We strongly believe that both sham-CPAP and attention control are safe and appropriate, and that this proposed modification would not impact subject safety.

I have discussed this proposed change with the study co-Investigators and the data coordinating center and have gotten approval from the DSMB(attached). I recognize that this is a major protocol change that will require NIH/NHLBI approval and am writing this letter to formally request approval. As part of this request we have outlined a detailed rationale and analytical plan that takes this proposed change into consideration. Attached to this letter is also a revised Protection of Human Subjects Form that addresses this proposed modification, with Track Changes to highlight the edits.

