Rationale:

Currently our study, in part, consists of a randomized controlled trial of Auto-CPAP vs. Sham CPAP in pregnancy. As of 2/14/17, we have screened 309 participants, enrolled 228, randomized 43 to auto-CPAP or sham CPAP, and assigned 96 to the control group for observation only. We are very pleased with our study recruitment and data collection processes. We are recruiting on schedule and have excellent retention. The over-arching goals of my study were to provide mechanistic insights on how SDB impacts pregnancy and to provide preliminary/feasibility data to inform the practical and scientific aspects of a CPAP and pregnancy trial. For the latter, I would like to continue to make iterative changes to the protocol to understand best practices to optimize CPAP use in pregnancy as part of a clinical trial. To improve compliance to CPAP among randomized subjects, we have added a monetary incentive and we have demonstrated a positive effect from this modification, but, given recent data from other sleep cohorts, I remain wary about how having a sham arm may be hindering compliance. My co-investigators and I are requesting approval for this modification because we believe that it will enhance the scientific value of our study data. The CPAP trial component of our study (Aims 2 and 3 outlined below) is a pilot study not designed to definitively determine effectiveness, but rather determine the feasibility and acceptability of a CPAP trial in pregnancy and see if a treatment effect is possible to consider for a larger study. To that end, we strongly believe that any modification that leads to increased adherence to treatment will be of great value.

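### If compliance means CPAP use, the treatment-by-compliance MANOVA cannot separate its terms in the CPAP versus sleep hygiene comparison

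*SAP*

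**What the plan says.** SAP section C (Analysis Plan) names the comparison for the revised Aims 2 and 3: "The treatment effects of sleep hygiene vs. active CPAP on the vector of cardiovascular risk factors" are to be compared by MANOVA. Analysis is by intention to treat, and "exploratory analyses would be conducted on the per protocol subgroup". Baseline imbalances may be adjusted for: "If differences in baseline characteristics are observed, the characteristics would be included in the MANOVA". After saying that the plan will be repeated per protocol, the SAP states that the MANOVA has "main effects for treatment group and an indicator of the level of compliance as well as the two-way interaction". Aim 3 follows the same construct, with the placental profile as outcome.

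The SAP does not define the compliance indicator. Where it explains the redesign, it uses the word for CPAP: in the Request, "we believe it will enhance compliance with CPAP"; in the Rationale, "To improve compliance to CPAP among randomized subjects, we have added a monetary incentive". The footnote to that incentive, in section 5.7 of both the SOAP1 and SOAP2 manuals, holds the only definition in the documents: "Compliance is defined as using the CPAP a minimum of 4 hours per day for at least 5 out of 7 days". The SOAP2 manual restricts the incentive to CPAP participants.

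In SOAP2, women assigned to sleep hygiene receive general information (section 5.2) and monthly reminders (5.5). At delivery a machine is collected only where one was issued (5.6). No adherence measure is described for this arm.

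**The concern.** The specified model suits a trial in which both arms have a device. It has been carried into a phase in which only one arm has one. If compliance is CPAP use, it cannot vary in the hygiene arm, so the data cannot support separate treatment, compliance and interaction terms.

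Better CPAP compliance is the stated reason for the redesign, so readers will look to this model. Software that drops a redundant column still prints a coefficient labelled treatment. That number could be taken as the CPAP effect when the larger trial is planned, although it does not estimate the randomized contrast.

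**Working it through.** **Inputs from the documents.** 18 women to CPAP and 18 to sleep hygiene, and 45 women in the CPAP versus sham phase (SAP, Aim 2); the model terms (SAP section C); the compliance definition (section 5.7 footnotes of both manuals). **Assumed:** a 23/22 split of the 45; compliance of 30 to 70%; a prognostic gap between compliers and non-compliers of 0.5 to 1.0 SD.

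The SAP gives no figure for the compliance model. Its detectable effect of 1.52 concerns the MANOVA with four outcomes and does not enter here.

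**Step 1: the design matrix.** Let T = 1 for CPAP and C = 1 for compliant, with k compliant CPAP women.

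| Group | n | T | C | T×C |
|---|---|---|---|---|
| CPAP, compliant | k | 1 | 1 | 1 |
| CPAP, not compliant | 18 − k | 1 | 0 | 0 |
| Hygiene, coded 0 | 18 | 0 | 0 | 0 |
| Hygiene, coded 1 (alternative) | 18 | 0 | 1 | 0 |

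There are three groups and four parameters.

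- Hygiene coded 0: C = T×C in every row. Rank is 3 of 4. T is estimable; C and T×C are not.
- Hygiene coded 1: C = 1 − T + T×C in every row. Rank is 3 of 4. None of the three terms is estimable.
- Hygiene coded missing: 18 rows remain, T is constant and T×C = C. Rank is 2.
- Per-protocol set (CPAP compliers plus hygiene): rank is 2 of 4. Coded 0, T = C = T×C; coded 1, C is constant and T×C = T.

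The rank is 3 for every k from 1 to 17 under either coding (34 cases). It is also 3 with hours of use or a three-level score and hygiene set to 0. Baseline covariates do not help: with 1, 2 and 4 covariates the rank is 4 of 5, 5 of 6 and 7 of 8.

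**Step 2: what the surviving treatment coefficient means.** With hygiene coded 0 and the duplicate column dropped,

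T coefficient = mean(non-compliant CPAP) − mean(all hygiene).

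With outcome SD 1 and k = 9, its standard error is √(1/9 + 1/18) = 0.41 SD, against √(1/18 + 1/18) = 0.33 SD for the intention-to-treat contrast.

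**Step 3: illustrative bias with no true effect.** Let p be the proportion compliant and g the gap by which compliers are healthier, whatever their treatment. Randomization puts the same expected proportion p of would-be compliers in the hygiene arm, so its mean lies pg above that of the non-compliers. Hence

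- T coefficient: 0 − pg = −pg
- compliers versus hygiene: g − pg = (1 − p)g

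At p = 0.5 and g = 0.5 these are −0.25 and +0.25 SD. A simulation (6,000 replicates, 18 per arm, positive favours CPAP, Monte Carlo error at most 0.007) agrees with the formulas to about 0.01. The adjusted columns assume that one measured covariate carries half the gap.

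| p | g | T coefficient | Compliers vs hygiene | T, adjusted | Compliers vs hygiene, adjusted |
|---|---|---|---|---|---|
| 0.3 | 0.5 | −0.15 | +0.34 | −0.08 | +0.16 |
| 0.5 | 0.5 | −0.25 | +0.25 | −0.12 | +0.12 |
| 0.7 | 0.5 | −0.35 | +0.16 | −0.17 | +0.07 |
| 0.3 | 1.0 | −0.30 | +0.70 | −0.14 | +0.30 |
| 0.5 | 1.0 | −0.49 | +0.51 | −0.22 | +0.22 |
| 0.7 | 1.0 | −0.70 | +0.30 | −0.32 | +0.13 |

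With g = 0 both contrasts are about 0. The intention-to-treat contrast is about 0 throughout.

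**Step 4: where the model does work.** In the sham phase both arms have a unit that transmits data (SOAP1 manual, section 2). With an assumed 23/22 split, the rank is 4 of 4 whenever each arm has at least one complier and one non-complier. It is also 4 of 4 if hygiene women have a varying measure of their own. A model with all three groups (active, sham, hygiene) has rank 5 of 6: the hygiene interaction is still lost.

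**The case against.** The strongest objection is that the premise is inferred. The SAP says only that there is an indicator of compliance; the definition used here was written for an incentive payment. Elsewhere the SAP speaks more generally of compliance with, or adherence to, treatment. Section C presents itself as a summary, and both manuals place the statistical models in a Protocol that is not among the documents. The Apnea Survey and Sleep Questionnaire also reach hygiene women. This stands as a condition on the finding, but no available document makes either form a compliance measure. If one is intended, the SAP still has to name it.

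Hygiene women are told their diagnosis and given a sleep specialist's contact, so some could obtain CPAP outside the study, which would break the exact alias. No collection of such use is described.

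The compliance sentence might be meant for the per-protocol subgroup only; that lowers the rank to 2. Pooling sham and hygiene as one control gives rank 4 of 4, but the SAP does not say this, and control-arm compliance would then be informed by sham users alone.

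It is fair that dropping one redundant column loses no data and leaves a valid three-group description. The difficulty is the label on the remaining coefficient. It is also fair that the bias sizes rest on assumed rates and gaps, that −0.25 SD is smaller than that coefficient's standard error of 0.41 SD, and that complier selection affects any per-protocol comparison. The rank result needs none of those figures.

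**Conclusion.** The concern holds, on the condition that CPAP use is the compliance measure and no CPAP use is recorded in the hygiene arm. Under that condition the failure is algebraic: it does not depend on sample size, alpha or the compliance rate, provided the CPAP arm includes both compliers and non-compliers. If all 18 comply or none does, the rank falls to 2.

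The bias in Step 3 is an illustration only. Over 30 to 70% compliance and gaps of 0.5 to 1.0 SD, the treatment coefficient runs from −0.15 to −0.70 SD (against CPAP), and compliers versus hygiene from +0.16 to +0.70 SD (in favour of CPAP).

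The weight is moderate and the point should be fixed: intention to treat is the basis of analysis and is unaffected, the per-protocol work is exploratory, and Aims 2 and 3 are a pilot. Confidence is medium because the indicator is undefined and the separate Protocol was not available.

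**What to change.** State in SAP section C, for Aims 2 and 3:

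1. The intention-to-treat MANOVA for CPAP versus sleep hygiene has no compliance main effect or interaction.
2. The treatment-by-compliance model is confined to the CPAP versus sham phase and is exploratory.
3. In the hygiene phase, CPAP use is related to outcome within the CPAP arm only, as a non-randomized analysis. Compliers versus hygiene is not reported as a treatment effect.
4. If a hygiene-adherence measure is intended, name it and define per protocol for that arm. The model would then be estimable, but compliance would mean a different behaviour in each arm, and the SAP should say so.

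The cost is a few sentences and no new data, since CPAP usage is already transmitted. The trial gives up a per-protocol effect and an interaction test in the hygiene phase, so the compliance model rests on the 45 women of the sham phase.
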